Effect of Different Volumes of Training of Pilates Exercises on
Muscle Strength, Postural Balance, Flexibility, Functional Autonomy,
Depressive Symptoms and Pulmonary Function on Elderly

NCT03791502

SEPTEMBER 17, 2019

ABSTRACT

Background: aging is a progressive process that leads to decreased muscle strength and mobility, slowness in reaction time and impaired balance, compromising autonomy and quality of life. **Objective:** to compare the effect of different volumes of Pilates training on strength, balance, flexibility, functional autonomy, depressive symptoms and pulmonary function in the elderly community. **Method:** it will be a randomized clinical trial with elderly of both sexes. The Group A (GA) exercises with smaller volume and greater variability of exercises, Group B (GB) greater volume and lower variability and Group C (CG) will maintain its usual activities. The intervention will occur twice a week for 60 minutes for 12 weeks. In order to evaluate the strength, Biofeedback System for resting exercises with elastic overload (E-lastic®), 30-second chair stand test (30-s CST) and Palmar gripper dynamometer will be used. The balance will be evaluated in the semi-tandem, tandem and unipodal positions, by the Timed Up and Go (TUG) and Step Test. Flexibility will be assessed using the Wells database, functional autonomy, dressing-gown test (VTC), depressive symptoms by the Geriatric Depression Scale (GDS) and lung function by many vacuum and spirometry. Data distribution will be done using the Shapiro-Wilk test, frequency and percentage calculation for categorical variables, the mean and standard deviation for continuous variables with normal, median, and interquartile distribution for variables with non-normal distribution. For comparison of the three groups will be used ANOVA One Way with post hoc of Bonferroni or Kruskal Wallis with Bonferroni correction, comparison of the continuous variables at moments before and after twelve weeks of intervention the Student's t-test paired or Wilcoxon and for the comparison of the categorical variables the test chi-square. **Expected results:** significant improvement of outcomes in both intervention groups compared to CG, however, the group with higher training volume and lower exercise variability will have a greater effect than the group with lower volume and greater variability of exercises. **Keywords:** Exercise Movement Techniques, Elderly, Aging, Muscular Strength, Balance, and Flexibility

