the included studies presented the prescribed volume: ten replicates (11) and three series of ten repetitions (15). Some studies have also described the volume: two sets of ten repetitions (16), two to four sets of 15 to 20 seconds of contraction for isometric exercises and 15 to 20 repetitions for dynamic exercises (17). A single series of 10 replicates with a 30-second interval between the series (18,19). It is known that the literature suggests for the muscular strength gain in the elderly a training volume of two to three sets per exercise, seven to ten repetitions per set and a moderate to high intensity (8,20) and as noted most Pilates exercise programs have not followed these recommendations.

The aim of the study is to compare the effect of different volumes of Pilates exercise training on muscle strength, postural balance, flexibility, functional autonomy, depressive symptoms and lung function in the elderly community. We believe that Pilates exercises will have beneficial effects for the elderly, but our hypothesis is that the group that performs a greater volume of Pilates exercise training will have a greater improvement in the investigated outcomes than the group with the lowest volume.

Methods

Type and location of study

This is a randomized clinical trial, which will be conducted at a Pilates studio in Goiânia.

Participants

The elderly will be invited through advertisements in social networks, local media, and posters distributed in the centers of coexistence of the elderly, health centers and churches and will be selected, considering the possibility of 20 % of sample losses, the first 57 eligible participants according to the following inclusion criteria:

- Age between 60 and 85 years;
- To present cognitive aptitude according to the Mental State Mini-Exam (MMSE);
- Independent walking, without the use of auxiliary walking devices;
- Not participating in other physical intervention research;

- Not having undergone physiotherapeutic treatment and not having participated in a structured physical activity in the previous month;
- Do not present neurological diseases, history of fractures or recent surgeries and serious cardiorespiratory diseases.

Participants will be excluded:

- Failure to attend all stages of evaluation;
- They did not complete 80% of the intervention.

Outcomes and Measuring Instruments

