- Static postural balance: will be evaluated by measuring the time each participant can maintain in three progressively more difficult positions: semi-tandem, tandem and unipodal support. In all positions the individuals must be with their hands on their waist, the total time to stay in each position is 30 seconds and it will have 3 attempts in each position and the best time will be recorded. The evaluator will demonstrate the test once.
- Dynamic postural balance: to evaluate the dynamic balance, the Timed Up and Go (TUG) test and the Step Test will be used. The TUG starts with the participant sitting in the chair, in the "go" command, he gets up from the chair, walks 3 meters at a comfortable pace, turns around, goes back to the chair and sits down. It will be demonstrated once and then it will do a repeat for familiarization. In the Alternative Step Test, the participant is asked to make eight beats of the foot, alternating between right and left, on a step in front of him with a height of 18 cm. Time will be timed and used in the analyzes. The test should be performed in 10 seconds.

Flexibility

To evaluate the flexibility of the hamstring muscles will be used the Sit and Go Test, using the Wells bench, participants will remain without footwear, sitting with knees extended, shoulders flexed, elbows extended and hands overlapped. Participants should perform trunk flexion at the front, perform a forced expiration, and move the seat ladder as far as possible, this procedure will be performed three times and immediately noted by the evaluator, with the best.

Functional Autonomy

The functional autonomy of the upper limbs will be evaluated by the dressing test and a t-shirt. Initially, the evaluator will explain the test and the volunteer will do a brief training with two replicates. The execution time is marked in seconds and the shorter the execution time, the better the result. The subject must make two attempts, where the best performance attempt will be recorded.

Depressive symptoms

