Initially, everyone who agrees to participate in the study will sign the informed consent form, then the data concerning the variables: cognitive ability, sociodemographic, clinical characterization, and anthropometric measurements will be collected. All participants will be evaluated for muscle strength, balance, flexibility, functional autonomy, depression and lung function before and after the intervention, including those who do not complete 80% of their presence during the intervention. For the self-report questionnaires an evaluator will be trained and for the performance questionnaires/tests two evaluators will be trained and they will be blind to the intervention. Subjects will be randomized into three groups. The randomization process will be done at random.org and concealment of the allocation will occur using opaque and sealed envelopes.

Statistical analysis plan

A sample size was calculated using the effect size identified in the comparison of the results concerning the post-intervention moment of the intervention and control groups, using data from the literature (18,25,26). The calculation indicated the need for a sample size of 15 participants per group for a power of 80% and an alpha error of 0.05 in the intergroup comparison analyzes for the variables muscle strength, balance, and flexibility.

Initially, the distribution of the data will be determined by means of the Shapiro-Wilk normality test. Subsequently, the descriptive analysis will be performed with frequency and percentage calculation for the categorical, mean and standard deviation data for continuous data with normal distribution and for median and interquartile data for continuous data with non-normal distribution.

For the comparison of the three groups for the performance of the continuous data, the ANOVA One Way test with post hoc of Bonferroni or Kruskal Wallis with Bonferroni correction (according to the normality of the data) will be used. The t-test of paired student or Wilcoxon (according to the normality of the data) will be used to compare the continuous data at the before and after moments in each group. Comparison of categorical data will be done using the chi-square test. For each primary and secondary outcome, the values observed in each group will be described, the size of the estimated effect along with its accuracy (eg, 95% confidence interval). It will be adopted 5% significance level.

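### The 80% power statement rests on an intervention-versus-control effect and gives no basis for the high- versus low-volume comparison that the trial states as its hypothesis

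*Combined protocol and SAP*

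**What the plan says.** All places are in the combined protocol and SAP.

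- **Sample size** (Statistical analysis plan): the calculation uses the "effect size identified in the comparison of the results concerning the post-intervention moment of the intervention and control groups", taken from the literature, and reports the "need for a sample size of 15 participants per group for a power of 80% and an alpha error of 0.05". It is said to serve intergroup comparisons of muscle strength, balance and flexibility. No effect size, SD, test or sidedness is given.
- **Hypothesis** (Introduction, last paragraph before Methods): "our hypothesis is that the group that performs a greater volume of Pilates exercise training will have a greater improvement" than the lowest-volume group.
- **Expected results** (Abstract): "significant improvement of outcomes in both intervention groups compared to CG" and, in addition, "the group with higher training volume and lower exercise variability will have a greater effect than the group with lower volume".
- **Analysis** (Statistical analysis plan): one-way ANOVA with a Bonferroni post hoc, or Kruskal-Wallis with Bonferroni correction, depending on normality. The variable entered is described only as "For the comparison of the three groups for the performance of the continuous data", which does not say post-intervention value or change.
- **Enrolment** (Participants): "considering the possibility of 20 % of sample losses, the first 57 eligible participants".

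**The concern.** The plan has two between-group expectations: both Pilates groups beat control, and GB beats GA. The effect size used can support the first. It cannot stand in for the second, because control participants keep their usual activities, whereas GA and GB both receive supervised Pilates with the same session length, frequency, duration and effort target. The difference between two active programmes need not resemble the difference between Pilates and no programme.

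Because the 80% is attached to intergroup comparisons in general, a reader can take it to cover the hypothesis. A non-significant GB-GA result could then be read as evidence that training volume does not matter, when the trial had little chance of showing that it does.

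Two further gaps bear on the figure. The alpha quoted is 0.05, while the planned post hoc spreads 0.05 over three pairs. The planning effect is on post-intervention values, while the hypothesis speaks of improvement.

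**Working it through.** **Inputs from the plan:** 15 per group analysed, three groups, power 80%, alpha 0.05, Bonferroni post hoc, 20% losses, 57 enrolled.

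**Assumptions:** two-sided tests, normal data with equal SDs, and a Bonferroni level of 0.05/3 = 0.0167 per pair.

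**1. The plan's own figures.** The enrolment step reproduces: 3 × 15 = 45, and 45/0.80 = 56.25, rounded up to 57 (19 per group). The 15 cannot be reproduced without an effect size, so I solved for the effect that it implies.

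**2. Implied effect and detectable difference.** The test statistic is noncentral t with noncentrality d × √(n/2) = d × √7.5. I used 28 df (two groups) and 42 df (pooled ANOVA error).

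| Level | d for 80% power, n = 15 per group |
|---|---|
| 0.05, one pair, unadjusted (28 df) | 1.06 |
| 0.05/3 (42 df; 28 df) | 1.22; 1.25 |
| 0.05, three-group F test | f = 0.480 |

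For the F-test reading, f = 0.480 means an active-control difference of 1.018 SD if GA and GB are equal (f × 3/√2), or a GB-control difference of 1.175 SD if the groups are equally spaced (f × √6).

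**3. GB versus GA at half the implied effect (assumption), post-intervention values, level 0.05/3.**

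| How 15 was obtained | Half effect (SD) | Power |
|---|---|---|
| Unadjusted t, d = 1.06 | 0.53 | 15.5% (28 df), 16.1% (42 df) |
| Bonferroni t, d = 1.22 to 1.25 | 0.61 to 0.62 | 21.9% |
| F test, GA = GB | 0.51 | 14.8% |
| F test, equal spacing | 0.59 | 20.1% |

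Without Bonferroni, 0.53 SD still has only 29%. At 25% and 75% of d = 1.06, Bonferroni power is about 5% and 37% to 39%.

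**4. Change scores.** With equal pre and post SDs, SD(change) = SD(post) × √(2(1 − r)). For 0.53 post-intervention SD at 0.05/3 and 42 df:

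| r | Standardised change, 0.53/√(2(1 − r)) | Power |
|---|---|---|
| 0.5 | 0.53 | 16% |
| 0.7 | 0.68 | 28% |
| 0.8 | 0.84 | 43% |
| 0.9 | 1.19 | 77% |

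The correlation needed for 80% is r = 1 − (0.53/1.224)²/2 = 0.906 (0.910 with 28 df). If the implied effect was 1.22, half is 0.612 and r = 0.875.

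**5. Outcomes that did not set the sample size.** The figures above use the effect of whichever outcome required 15. If another outcome needed only 10 per group (assumption), its implied effect is 1.32 SD. At 15 per group and 0.05/3 it has 25% to 26% power at half effect and 85% to 87% versus control.

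**6. Against control, for the outcome that set 15.** If 0.05 was an unadjusted two-sided pairwise level, d = 1.06 has 64% to 66% power at 0.05/3. If Bonferroni was already included, there is no shortfall. The plan does not allow a choice between these.

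**7. Precision.** The expected 95% CI half-width for GB-GA is t × √(2/15): 2.048 × 0.365 = 0.75 SD (28 df) and 2.018 × 0.365 = 0.74 SD (42 df). With Bonferroni it is 0.93 and 0.91 SD.

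**The case against.** The plan discloses where its effect came from, in the sentence before the 80%, and superiority of both Pilates groups over control is one of its expected results. Read that way, the calculation fits part of the aim, and the one arithmetic step that can be checked is right. This stands: the fault is a missing basis for one comparison, not a wrong sum.

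The analysed number may exceed 15. Losses of 20% are only a possibility, everyone is to be reassessed, and intention-to-treat analysis is allowed if necessary. With 19 per group the Bonferroni detectable difference is 1.08 to 1.09 SD, and power versus control at d = 1.06 rises to 77% to 78%. That matters for the control comparisons. GB versus GA at 0.53 SD reaches only 20% to 21% (28% to 29% at 0.612 SD). Excluding participants who complete less than 80% of the intervention, as the Participants section provides, pulls the other way.

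Sidedness is not stated. One-sided planning would imply d = 0.93, which lowers the two-sided Bonferroni power to about 12% at half effect and 51% to 53% versus control.

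Half the effect is a chosen illustration. That is fair, and the correlations and the 10-per-group outcome are also assumptions. The detectable difference and the CI half-width do not depend on any of them.

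Finally, the normal-theory figures may not apply to every outcome. In static balance "the total time to stay in each position is 30 seconds and it will have 3 attempts in each position", so a ceiling could lead to the rank test. The normal-theory figures are therefore limited to the ANOVA branch.

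**Conclusion.** The concern holds. The 80% is supported at most for intervention versus control. Nothing in the plan supports it for GB versus GA, and no Bonferroni allowance is documented. In the ANOVA branch with 15 per group and two-sided tests, GB would have to exceed GA by 1.22 to 1.25 SD of the analysed variable, roughly as much as the calculation implies Pilates exceeds control. The 15% to 22% figure depends on three conditions: two-sided planning, a GB-GA difference of half the implied effect, and analysis of post-intervention values. Change scores could give adequate power only with a pre-post correlation near 0.9, which the plan does not state. Whether power versus control also falls short cannot be determined.

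**What to change.** In the Statistical analysis plan section:

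1. Limit the 80% statement to intervention versus control, and give for each outcome the effect size, SD, test, sidedness and alpha behind the 15.
2. State whether the three-group test uses post-intervention values or changes.
3. Add text such as: *For the ANOVA branch, with 15 per group, the GB-GA difference detectable with 80% power under the Bonferroni post hoc is about 1.22 to 1.25 SD of the analysed variable (post-intervention value or change, to be stated). The expected 95% CI half-width is about 0.75 SD (0.91 to 0.93 SD with Bonferroni). The trial is not powered for smaller GB-GA differences.*
4. Make no power statement for the Kruskal-Wallis branch unless it is calculated separately.
5. Report a non-significant GB-GA result as inconclusive unless its confidence interval excludes a difference named in advance. The plan already promises effect estimates with their precision, so this needs no new analysis.

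The cost is SAP wording and a less favourable power statement for GB versus GA. No participants are added.

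### A normality pre-test chooses each outcome's test and summary after the data are seen, no effect estimator is named for the rank route, and neither between-group route uses baseline

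*Combined protocol and SAP*

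**What the plan says.** All of this is in the Statistical analysis plan section; the Abstract repeats the scheme.

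- The first step is a pre-test: "Initially, the distribution of the data will be determined by means of the Shapiro-Wilk normality test". It also settles whether a variable is summarised by mean and SD or by median and interquartile range.
- Between groups, the plan uses "the ANOVA One Way test with post hoc of Bonferroni or Kruskal Wallis with Bonferroni correction (according to the normality of the data").
- Within groups: "The t-test of paired student or Wilcoxon (according to the normality of the data) will be used" for before against after.
- For every primary and secondary outcome the plan promises "the size of the estimated effect along with its accuracy (eg, 95% confidence interval").
- The sample size is "15 participants per group for a power of 80% and an alpha error of 0.05", derived "using the effect size identified in the comparison of the results concerning the post-intervention moment of the intervention and control groups". No effect size or SD is given.

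Evaluation procedures has every outcome measured before and after the intervention, so a baseline value exists for each. Neither between-group test includes it.

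**The concern.** The documents leave the pre-test undefined in five respects: raw values, residuals or differences; per arm or pooled; before, after or both; its own significance level; and what to do if arms or time points disagree. No outcome therefore has a fixed analysis until its data have been examined. Two similar outcomes, such as two of the muscle groups measured with the same device, could be reported with different tests and on different scales.

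Three consequences follow.

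- **Effect estimate.** The Introduction's hypothesis is that the higher-volume group (GB) improves more than the lower-volume group (GA). The key result is therefore the size of the GB-GA difference, and for an outcome sent to ranks the plan does not say how that size is estimated.
- **Paired test.** The paired t-test needs normal differences. If the pre-test is run on raw values, it can send an outcome to Wilcoxon for no relevant reason.
- **Baseline.** With 15 per arm, leaving out a baseline value that is already collected gives up precision on either route.

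**Working it through.** **The plan's own figures.** 15 × 3 = 45, and 45/(1 − 0.20) = 56.25, rounded up to 57, which matches the enrolment in Participants. The 15 per group cannot be reproduced because no effect size is given. Solving backwards, 15 per group with 80% power at two-sided 0.05 implies a standardised difference of 1.06 (t-test). Two-sidedness is assumed. The power check below uses 1.06.

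**1. How often the route switches.** Assumptions: Shapiro-Wilk at 0.05, 15 per arm, and rejection in any of three arms sends the outcome to ranks. If one arm rejects with probability p, P(rank route) = 1 − (1 − p)³. The distributions are assumed, since the documents give none. Simulation used 4,000 trials per case.

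| Shape | p, one arm | Formula | Simulated, any arm | Arms disagree | Pooled test, n = 45 |
|---|---|---|---|---|---|
| Normal | 0.050 | 1 − 0.950³ = 0.143 | 0.139 | 0.139 | 0.046 |
| Log-normal, log SD 0.3 (skew 0.95) | 0.184 | 1 − 0.816³ = 0.457 | 0.452 | 0.446 | 0.527 |
| Log-normal, log SD 0.4 (skew 1.32) | 0.276 | 1 − 0.724³ = 0.620 | 0.626 | 0.606 | 0.756 |
| Log-normal, log SD 0.7 (skew 2.89) | 0.602 | 1 − 0.398³ = 0.937 | 0.938 | 0.713 | 0.988 |

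If baseline is tested as well, normal data give up to 1 − 0.95⁶ = 26.5%, treating the six tests as independent. The last two columns show that the unstated details matter: arms often disagree, and pooling changes the route.

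**2. Paired comparison.** One arm of 15, with log-normal raw values (log SD 0.3 / 0.5 / 0.7) and exactly normal changes. Raw pre or post values are rejected in 22 / 44 / 63% of trials; the differences are rejected in 5%. Counting two tests instead of one does not explain this, since two independent 5% tests give only 1 − 0.95² = 9.8%.

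**3. Error rate and power of the switching rule.** Simulated type I error is 4.6-5.7%. Omnibus power with arm means 0 / 0.53 / 1.06 SD:

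- Normal data: ANOVA 0.70, Kruskal-Wallis 0.67, switching rule 0.70.
- Log-normal, log SD 0.3: ANOVA 0.71, switching rule 0.74.
- Log-normal, log SD 0.6: ANOVA 0.74, switching rule 0.90.

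**4. What baseline would add.** Closed form for normal data:

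- f² = [(0 − 0.53)² + 0 + (1.06 − 0.53)²]/3 = 0.5618/3 = 0.1873, so λ = 45 × 0.1873 = 8.43. F(2, 42) then has power 0.71.
- Adjusting for a baseline with correlation r divides λ by 1 − r². At r = 0.5, λ = 8.43/0.75 = 11.24 and F(2, 41) has power 0.83. At r = 0.7, λ = 8.43/0.51 = 16.52 and power is 0.95.

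Simulation agrees: 0.70-0.72 for the planned rule, against 0.84 and 0.95 with adjustment.

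**5. Where adjustment does not win.** Log-normal, log SD 0.6, r = 0.5: linear model with baseline 0.81, ranks 0.89.

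**The case against.** The best defence is that both branches and the trigger are written down in advance, so this is a pre-stated conditional rule. Its type I error is near 5%, and for skewed data it beats ANOVA. For stance times capped at 30 s and the 0-15 depression score, it would often choose the rank method that a reviewer would want anyway. All of that stands.

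A reader might also infer several stronger points that the documents do not support.

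- **That the pre-test examines the wrong quantity throughout.** Residuals of a one-way ANOVA are values minus the arm mean, and Shapiro-Wilk ignores location. A per-arm test on raw values is therefore adequate for the planned ANOVA, in a mixed-sex sample too. The objection applies only to the paired test, and only if raw values are what is tested; the text does not say.
- **That the route is a coin toss at 15 per arm.** Rejection in one arm runs from 5% for normal data to nearly 100% for heavily capped times. It is near 50% only for some shapes.
- **That many outcomes would go to ranks.** The documents give no distributional data, so no count can be derived from them.
- **That the rank route cannot deliver the promised effect.** The promise covers every outcome, and a rank-based shift estimate with an interval could meet it. The gap is that none is named.
- **That switching costs power.** It does not, against ANOVA. The loss belongs to the missing baseline term.

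**Conclusion.** The point holds in limited form. The analysis route for each outcome is settled only after its data are seen, by a rule too loosely specified to be applied in one way. Under the any-arm reading at 15 per arm, about 14% of exactly normal outcomes and about 45% of moderately skewed ones would go to ranks. The paired test can be misrouted if raw values are tested, and no estimator is named on the rank route for the promised effect with its interval.

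This is a matter of pre-specification, interpretability and precision. It is not a threat to the 5% level. The gain on offer, from about 0.70-0.72 to 0.84 or 0.95 omnibus power, comes from the baseline term. It rests on normal data, the assumed arm means, baseline correlations of 0.5 and 0.7, and the between-group test being run on 12-week values, as the sample-size paragraph suggests. The change is worth making before analysis because it is nearly free.

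**What to change.** In the Statistical analysis plan section:

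1. Remove the clause that makes the choice of test depend on normality.
2. For each continuous outcome, pre-state one linear model of the 12-week value on arm plus the baseline value. Report the GB-GA, GA-CG and GB-CG differences with 95% confidence intervals, keeping the Bonferroni correction.
3. Name in advance the bounded outcomes (the three stance times and the depression score) that will use a rank or ordinal method, with its effect measure and confidence interval.
4. Use normality checks descriptively only: on model residuals and, if within-group comparisons are kept, on the paired differences.
5. Give mean/SD and median/IQR for every continuous variable at both times, so that the summary does not depend on a test.
6. Add a permutation or rank-based sensitivity analysis.

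The cost is one paragraph and no new data. The downside is some loss of power for a strongly skewed outcome weakly correlated with its baseline (0.81 against 0.89 in the case above), which is why item 6 is included.

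### The three-group comparison names no baseline covariate and does not say whether post values or changes are analysed, so it gives up precision that the planned baselines would supply

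*Combined protocol and SAP*

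**What the plan says.** Under Statistical analysis plan, the between-group test is given as "For the comparison of the three groups for the performance of the continuous data, the ANOVA One Way test with post hoc of Bonferroni". When normality fails, the same sentence switches to a rank test: "Kruskal Wallis with Bonferroni correction (according to the normality of the data) will be used". No covariate is named and the response variable is not defined. The same section promises, for each outcome, "the size of the estimated effect along with its accuracy (eg, 95% confidence interval", without saying on which scale the effect is measured.

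Baselines will exist. Under Evaluation procedures: "All participants will be evaluated for muscle strength, balance, flexibility, functional autonomy, depression and lung function before and after the intervention". The analysis section explicitly uses the before-and-after pair only in tests within each group: "The t-test of paired student or Wilcoxon (according to the normality of the data) will be used to compare the continuous data". The Abstract repeats this structure and adds nothing that settles the response.

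Two statements bear on the intended response. The sample size took its effect from "results concerning the post-intervention moment of the intervention and control groups". The hypothesis at the end of the Introduction is that the group with "greater volume of Pilates exercise training will have a greater improvement in the investigated outcomes than the group with the lowest volume".

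**The concern.** Each continuous outcome is measured twice, yet the randomised comparison as written makes no stated use of the first measurement. When baseline and post values are correlated, adjusting for baseline removes variance that a post-value comparison leaves in. It also avoids the noise that a change score adds when the correlation is low.

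This matters most for GB against GA, the contrast in the hypothesis. It compares two active programmes, so its difference may well be smaller than the intervention-versus-control difference behind the sample size, and there are only 15 analysed participants per group.

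A second, lesser issue is that an undefined response leaves room to choose between post values and changes after the data are seen, and leaves the promised effect estimate without a defined scale.

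**Working it through.** **Inputs from the documents.** 15 per group, 80% power, alpha 0.05, three groups, Bonferroni post hoc comparisons (Statistical analysis plan); 20% losses and "the first 57 eligible participants" (Participants).

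**The plan's own figures.** Enrolment reproduces: 45/(1 - 0.20) = 56.25, rounded up to 57, or 19 per group if allocation is equal. The 15 per group cannot be reproduced, because no effect size or SD is given. Solving backwards with a two-sided two-sample t test, 15 per group has 80% power for a difference of 1.06 SD.

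**Assumptions.** GB-GA difference 0.53 SD (half of 1.06); baseline-post correlation rho of 0.3, 0.5, 0.7 or 0.8; equal SDs at both times; the same rho in every group; a linear relation; two-sided tests; pairwise alpha 0.05/3 = 0.0167.

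**Formulas.** Residual variance relative to the post-value variance is 1 for post values, 2(1 - rho) for changes and 1 - rho² for baseline-adjusted post values (ANCOVA). Power comes from the noncentral t distribution with noncentrality 0.53/√factor × √(15/2). The pooled three-group error has 42 df, or 41 df for ANCOVA. The closed form ignores the cost of estimating the slope and of chance baseline imbalance, so ANCOVA was also simulated (100,000 trials per rho).

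| rho | factor: change / ANCOVA | post | change | ANCOVA, closed form | ANCOVA, simulated |
|---|---|---|---|---|---|
| 0.3 | 1.40 / 0.91 | 16.1% | 11.4% | 17.8% | 17.4% |
| 0.5 | 1.00 / 0.75 | 16.1% | 16.1% | 21.9% | 21.2% |
| 0.7 | 0.60 / 0.51 | 16.1% | 28.0% | 33.3% | 32.3% |
| 0.8 | 0.40 / 0.36 | 16.1% | 43.0% | 47.6% | 46.7% |

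Using the simulated column, ANCOVA gains about 1, 5, 16 and 31 points over post values, and about 6, 5, 4 and 4 points over changes.

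**Interval width.** The Bonferroni-matched half-width is t × √(2 × factor/15), with t about 2.49 (42 df) or 2.50 (41 df). In SD units it is 0.91 for post values; 1.08, 0.91, 0.71 and 0.58 for changes; and 0.87, 0.79, 0.65 and 0.55 for ANCOVA.

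**Other settings (closed form).** With 19 per group and no losses, power at 0.05/3 is 21% for post values, 15% to 55% for changes and 23% to 60% for ANCOVA. For the full 1.06 SD at 15 per group and alpha 0.05 (two-group t test), it is 80% for post values, 66% to 99% for changes and 84% to 99.7% for ANCOVA.

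**Open choice.** In simulation at 0.53 SD and 0.05/3, exactly one of the post and change tests is significant in about 16%, 20%, 28% and 39% of trials at the four correlations. The two were significant in opposite directions in essentially none. With no true difference, reporting whichever test is significant raises the pairwise error from 1.7% to about 3%.

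**Bounded outcomes.** The figures above do not carry over to the Kruskal-Wallis branch. For a time capped at 30 seconds, with 31% assumed at the cap at baseline, the planned rank test has 12% to 14% power, and a rank analysis adjusted for baseline rank has 14%, 17%, 23% and 31%. With 69% at the cap and rho 0.3 to 0.5, both have about 7%. With 84% at the cap they have about 2.8% and 3.1% to 3.7%.

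**The case against.** The best reply is that post values are the natural reading. The sample size rests on a post-intervention comparison, before-and-after data are assigned to a separate test in each group, and the mention of improvement in the hypothesis is ordinary prose. On that reading the selection argument largely falls away, and what remains is a valid test with its nominal power intact. Much of this stands: the text does lean towards post values, so the open choice is secondary. But the sample-size sentence describes where a literature effect came from and does not define this trial's response. If post values are meant, that is also the choice that loses most from rho 0.7 upwards.

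It is also fair that rho and the 0.53 SD are not in the documents, and that at rho 0.3 the gain over post values is about one point. The recommendation does not depend on knowing rho, since ANCOVA was ahead of both alternatives at every value checked; the size of the benefit does.

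Four stronger readings are tempting and not supported:

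- That post and change analyses would contradict each other. They differ in which one crosses the threshold, not in direction.
- That omitting baseline biases the comparison or breaks the stated 80% power. It does neither.
- That the authors will infer group differences from the within-group paired tests. The plan does not say so.
- That adjustment raises power for every stance time. The Postural balance section describes positions of increasing difficulty and records the best of three attempts, so the share at the cap will differ between them.

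**Conclusion.** The point holds as a gap in specification and efficiency. The response variable is unstated, no baseline covariate is named, and a more precise analysis is available from data already to be collected. For a GB-GA difference of 0.53 SD at 15 per group and 0.05/3, adjustment moves power from about 16% (post values) to about 17% at rho 0.3 and 46-47% at rho 0.8. Against changes the advantage is 4 to 6 points. Even the adjusted analysis stays below 50% in this setting, so adjustment helps the main contrast without making it well powered. These figures rest on the assumed difference, correlations, equal SDs and linearity, and apply to the ANOVA branch only. The change should be made before outcome data are seen, but its absence does not invalidate the trial.

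**What to change.** - Name the post-intervention value as the response. For each continuous outcome, make the between-group analysis an ANCOVA of the post value on group, with that outcome's own baseline as covariate. The planned SPSS software can fit this.
- Report adjusted GB-GA, GB-CG and GA-CG differences (CG is the control group). Keep the Bonferroni correction for the three pairs and give Bonferroni-adjusted intervals, so that interval and test agree. Ordinary 95% intervals may be added if labelled unadjusted.
- Where the normality rule would have led to Kruskal-Wallis, use the baseline-adjusted counterpart: regress the rank of the post value on group and the rank of baseline. State that this test decides significance and that any linear adjusted difference shown beside it is descriptive. Claim no general power gain for stance times; it may be negligible when most participants reach 30 seconds.
- Keep the within-group paired tests as descriptive.

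The cost is one degree of freedom per analysis and revised wording in the analysis section. No additional measurement is needed.
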